## 7 NIH REPORTING REQUIREMENTS / DATA AND SAFETY MONITORING PLAN

#### 7.1 **DEFINITIONS**

Please refer to definitions provided in Policy 801: Reporting Research Events found at: https://irbo.nih.gov/confluence/pages/viewpage.action?pageId=36241835#Policies&Guidance-800Series-ComplianceandResearchEventReportingRequirements.

### 7.2 OHSRP OFFICE OF COMPLIANCE AND TRAINING / IRB REPORTING

## 7.2.1 Expedited Reporting

Please refer to the reporting requirements in Policy 801: Reporting Research Events and Policy 802 Non-Compliance Human Subjects Research found at: https://irbo.nih.gov/confluence/pages/viewpage.action?pageId=36241835#Policies&Guidance-800Series-ComplianceandResearchEventReportingRequirements. Note: Only IND Safety Reports that meet the definition of an unanticipated problem will need to be reported per these policies.

## 7.2.2 IRB Requirements for PI Reporting at Continuing Review

Please refer to the reporting requirements in Policy 801: Reporting Research Events found at: https://irbo.nih.gov/confluence/pages/viewpage.action?pageId=36241835#Policies&Guidance-800Series-ComplianceandResearchEventReportingRequirements.

#### 7.3 NCI CLINICAL DIRECTOR REPORTING

Problems expeditiously reviewed by the OHSRP in the NIH eIRB system will also be reported to the NCI Clinical Director/designee; therefore, a separate submission for these reports is not necessary.

In addition to those reports, all deaths that occur within 30 days after receiving a research intervention should be reported via email unless they are due to progressive disease.

To report these deaths, please send an email describing the circumstances of the death to [contact] within one business day of learning of the death.

#### 7.4 NIH REQUIRED DATA AND SAFETY MONITORING PLAN

## 7.4.1 Principal Investigator/Research Team

The clinical and scientific research teams will meet on a weekly basis when participants are being actively treated on the trial to discuss each participant and overall progress of the study.

All data will be collected in a timely manner and reviewed by the principal investigator or a lead associate investigator. Events meeting requirements for expedited reporting as described in Section 7.2.1 will be submitted within the appropriate timelines.

The principal investigator will review adverse event and response data on each participant to ensure safety and data accuracy. The principal investigator will personally conduct or supervise the investigation and provide appropriate delegation of responsibilities to other members of the research staff.

Version Date: 7/10/2025

#### 8 SPONSOR PROTOCOL/SAFETY REPORTING

### 8.1 **DEFINITIONS**

#### 8.1.1 Adverse Event

Any untoward medical occurrence in a participant or clinical investigation subject administered a pharmaceutical product and which does not necessarily have a causal relationship with this treatment. An adverse event (AE) can therefore be any unfavorable and unintended sign (including an abnormal laboratory finding), symptom, or disease temporally associated with the use of a medicinal (investigational) product, whether or not related to the medicinal (investigational) product (ICH E6 (R2))

## 8.1.2 Serious Adverse Event (SAE)

An adverse event or suspected adverse reaction is considered serious if in the view of the investigator or the sponsor, it results in any of the following:

- Death,
- A life-threatening adverse event (see Section 8.1.3)
- Inpatient hospitalization or prolongation of existing hospitalization
  - A hospitalization/admission that is pre-planned (i.e., elective or scheduled surgery arranged prior to the start of the study), a planned hospitalization for pre-existing condition, or a procedure required by the protocol, without a serious deterioration in health, is not considered a serious adverse event.
  - A hospitalization/admission that is solely driven by non-medical reasons (e.g., hospitalization for patient or subject convenience) is not considered a serious adverse event.
  - Emergency room visits or stays in observation units that do not result in admission to the hospital would not be considered a serious adverse event. The reason for seeking medical care should be evaluated for meeting one of the other serious criteria.
- Persistent or significant incapacity or substantial disruption of the ability to conduct normal life functions
- A congenital anomaly/birth defect
- Important medical events that may not result in death, be life-threatening, or require hospitalization may be considered a serious adverse drug experience when, based upon appropriate medical judgment, they may jeopardize the participant or subject and may require medical or surgical intervention to prevent one of the outcomes listed in this definition.

### 8.1.3 Life-threatening

An adverse event or suspected adverse reaction is considered "life-threatening" if, in the view of either the investigator or sponsor, its occurrence places the participant or subject at immediate risk of death. It does not include an adverse event or suspected adverse reaction that, had it occurred in a more severe form, might have caused death. (21CFR312.32)

Version Date: 7/10/2025

## 8.1.4 Severity

The severity of each Adverse Event will be assessed utilizing the CTCAE version 5.0.

## 8.1.5 Relationship to Study Product

All AEs will have their relationship to study product assessed using the terms: related or not related.

- Related There is a reasonable possibility that the study product caused the adverse event.
   Reasonable possibility means that there is evidence to suggest a causal relationship between the study product and the adverse event.
- Not Related There is not a reasonable possibility that the administration of the study product caused the event.

## 8.2 ASSESSMENT OF SAFETY EVENTS

AE information collected will include event description, date of onset, assessment of severity and relationship to study product and alternate etiology (if not related to study product), date of resolution of the event, seriousness and outcome. The assessment of severity and relationship to the study product will be done only by those with the training and authority to make a diagnosis and listed on the Form FDA 1572 as the site principal investigator or sub-investigator. AEs occurring during the collection and reporting period will be documented appropriately regardless of relationship. AEs will be followed through resolution.

### SAEs will be:

- Assessed for severity and relationship to study product and alternate etiology (if not related to study product) by a licensed study physician listed on the Form FDA 1572 as the site principal investigator or sub-investigator.
- Recorded on the appropriate SAE report form, the medical record and captured in the clinical database.
- Followed through resolution by a licensed study physician listed on the Form FDA 1572 as the site principal investigator or sub-investigator.

For timeframe of recording adverse events, please refer to Section 6.1. All serious adverse events recorded from the time of first investigational product administration must be reported to the sponsor with the exception of any listed in Section 8.4.

### 8.3 Reporting of Serious Adverse Events

Any AE that meets protocol-defined serious criteria or meets the definition of Adverse Event of Special Interest that require expedited reporting must be submitted immediately (within 24 hours of awareness) to OSRO Safety. Any exceptions to the expedited reporting requirements are found in Section 8.4.

All SAE reporting must include the elements described in Section 8.2.

SAE reports will be submitted via an electronic SAE reporting system (e.g. HiLIT). In the event of system downtime or issues , SAE reports will be submitted using the CCR SAE Report form to the sponsor at: [contact]. CCR SAE report form and instructions can be found at: https://nih.sharepoint.com/:u:/r/sites/NCI-CCR-OCD-Communications/SitePages/Forms-and-Instructions.aspx?csf=1&web=1&e=uWBXtI

Version Date: 7/10/2025

Following the assessment of the SAE by OSRO, other supporting documentation of the event may be requested by the OSRO Safety and should be provided as soon as possible.

## 8.4 Waiver of expedited reporting to Sponsor (CCR)

As death/hospitalization due to disease progression are part of the study objectives (OS, DCR), and captured as endpoints in this study, they will not be reported in expedited manner to the sponsor. However, if there is evidence suggesting a causal relationship between the study drug and the event, report the event in in an expedited manner according to Section 8.3.

## 8.5 SAFETY REPORTING CRITERIA TO THE PHARMACEUTICAL COLLABORATORS

Reporting will be per the collaborative agreement.

#### 8.6 REPORTING PREGNANCY

All required pregnancy reports/follow-up to OSRO will be submitted to: https://nih.sharepoint.com/:u:/r/sites/NCI-CCR-OCD-Communications/SitePages/Forms-and-Instructions.aspx?csf=1&web=1&e=uWBXtI.

## 8.6.1 Maternal exposure

If a participant becomes pregnant during the course of the study, the study treatment should be discontinued immediately, and the pregnancy reported to the Sponsor no later than 24 hours of when the Investigator becomes aware of it. The Investigator should notify the Sponsor no later than 24 hours of when the outcome of the Pregnancy becomes known.

Pregnancy itself is not regarded as an SAE. However, congenital abnormalities or birth defects and spontaneous miscarriages that meet serious criteria (Section 8.1.2) should be reported as SAEs.

The outcome of all pregnancies should be followed up and documented.

### 8.6.2 Paternal exposure

Male participants should refrain from fathering a child or donating sperm during the study and for 3 months after the last dose of Minnelide .

Pregnancy of the participant's partner is not considered to be an AE. The outcome of all pregnancies occurring from 3 months after the last dose of Minnelide should, if possible, be followed up and documented. Pregnant partners may be offered the opportunity to participate in an institutional pregnancy registry protocol (e.g., the NIH IRP pregnancy registry study) to provide data about the outcome of the pregnancy for safety reporting purposes.

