## Appendix A

Version Date: 7/10/2025

	T
creatinine	$\leq 1.5 \times ULN$
OR	OR
measured or calculated b creatinine clearance (GFR can also be used in place of creatinine or CrCl)	≥ 45 mL/min for participant with creatinine levels >1.5 × institutional ULN
total bilirubin	≤1.5 ×ULN OR direct bilirubin ≤ULN for participants with total bilirubin levels >1.5 × ULN
AST (SGOT) and ALT (SGPT)	≤2.5 × ULN (≤5 × ULN for participants with liver metastases)
International normalized ratio (INR) OR - prothrombin time (PT) - activated partial thromboplastin time (aPTT)	≤1.5 × ULN unless participant is receiving anticoagulant therapy as long as PT or PTT is within therapeutic range of intended use of anticoagulants

ALT (SGPT) = alanine aminotransferase (serum glutamic pyruvic transaminase); AST (SGOT) = aspartate aminotransferase (serum glutamic oxaloacetic transaminase); GFR = glomerular filtration rate; ULN=upper limit of normal.

Note: This table includes eligibility-defining laboratory value requirements for treatment; laboratory value requirements should be adapted according to local regulations and guidelines for the administration of specific chemotherapies.

2.1.1.9 The effects of Minnelide on the developing human fetus are unknown. For this reason, women of child-bearing potential (WOCBP) and men must agree to use adequate contraception (hormonal or barrier method of birth control; abstinence) prior to study entry, for the duration of study participation, and for 6 months (women) and 3 months (men) after the last dose of trial treatment. Male participants must also refrain from donating sperm during this period. Should a woman become pregnant or suspect she is pregnant while she or her partner is participating in this study, she should inform her treating physician immediately.

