## **14.1.2 Toxicity**

Results from nonclinical pharmacological, pharmacokinetic, and toxicological studies evaluating Minnelide TM given intravenously or orally support the rationale for evaluation of Minnelide TM in cancer participants. Plasma concentrations of Minnelide TM and triptolide associated with key responses and exposure margins calculated against these key responses which reflect toxicological findings considered relevant or possibly relevant to human risk.

In definitive 28-day repeat dose toxicity studies, a no-observed adverse-effect level (NOAEL) for Minnelide TM in female dogs was identified to be 0.05 mg/kg/day and considered the highest non-

Version Date: 7/10/2025

severely toxic dose (HNSTD); the NOAEL for Minnelide TM in rats or male dogs could not be determined. Target organ toxicities indicated reproductive organ accumulation.

In humans, 42 participants with advanced GI tumors were given Minnelide TM intravenously in a phase 1 open-label dose-escalation safety, pharmacokinetic and pharmacodynamic study. Doses were given daily for 21 days followed by 7 days off or each day for 5 days with two days off for three weeks followed by a 7 day rest period. The primary reason for the discontinuation of treatment was disease progression. There were 6 deaths in the study, but these occurred after the study drug had ended and were within the 30-day follow-up period. The deaths that occurred during the study were found to be not related to the study drug, and were found to be related to progression of the participant's disease (pancreatic/gastric cancer). There was one participant who died from respiratory failure, and this was also found to be not related to use of the study drug. There were 3 participant who discontinued the study drug due to a treatment emergent adverse events (TEAEs). All instances were considered Grade 3, and two of these TEAEs were considered to be probably related to use of the study drug. These two cases were also considered (DLTs). These events included: cerebellar toxicity, embolism, and cerebellar dysfunction. A total of 28 Serious Adverse Events occurred in 17 participants and six were found to be related to the study drug.

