## 14.1.6 Incompatibilities

## 14.1.6.1 Pregnancy and Lactation

Teratogenic and nonteratogenic effects of Minnelide TM have not yet been investigated. Women who are pregnant or may become pregnant should not be administered Minnelide TM. In the event that Minnelide TM is inadvertently administered to pregnant participants, the clinician should discuss all available alternatives. Women of child-bearing potential and men must agree to use adequate contraception prior to study entry, for the duration of study participation and for 6 months (women) or 3 months (men) following last treatment. No data exist on the excretion of Minnelide TM in milk or on the effects of Minnelide TM on nursing infants.

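### Section 8.6.2 asks for follow-up of partner pregnancies only from the point where its own paternal exposure period ends; the two statements conflict and should be reconciled

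*Combined protocol and SAP*

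**What the plan says.** Section 8.6.2 (Paternal exposure) makes two statements about time.

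- On precaution: "Male participants should refrain from fathering a child or donating sperm during the study and for 3 months after the last dose of Minnelide".
- On follow-up: "The outcome of all pregnancies occurring from 3 months after the last dose of Minnelide should" be followed and recorded where that is feasible.

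The same section says that a partner's pregnancy does not count as an adverse event. It adds that pregnant partners may be offered entry to an institutional pregnancy registry, run under a separate protocol, and sets no time limit on that offer.

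The 3-month period for men appears in two other places. Section 2.1.1.9 asks for contraception "for 6 months (women) and 3 months (men) after the last dose of trial treatment", and Section 14.1.6.1 asks for it "for 6 months (women) or 3 months (men) following last treatment".

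Section 8.6.1 (Maternal exposure) asks for the outcome of every pregnancy, with no time restriction, and gives 24-hour deadlines for reporting both the pregnancy and its outcome to the sponsor.

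**The concern.** The precaution in 8.6.2 exists because drug exposure of the father might matter to a pregnancy. Follow-up of outcomes should serve the same purpose and so cover the same period. As written it covers what comes after that period.

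Staff who follow the sentence as it stands would have no instruction to trace a partner pregnancy conceived while the man was taking Minnelide or in the next 3 months. They would be asked to trace one conceived well after exposure, without any end date.

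The plan itself gives reasons to want the exposed cases. Section 2.1.1.9 says that effects on the human fetus are unknown, and Section 14.1.6.1 says that teratogenic effects have not been studied. Section 14.1.2 reports from 28-day studies in rats and dogs that "Target organ toxicities indicated reproductive organ accumulation". That last item is an animal finding in reproductive organs. It is not evidence of fetal harm or of harm passed on through the father, so it supports caution and no more.

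**Working it through.** The plan gives no figure to reproduce. The check is a comparison of periods. Let L be the date of a man's last dose.

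| Period | Starts | Ends | Source |
|---|---|---|---|
| Avoid fathering a child or donating sperm | during the study | L + 3 months | 8.6.2, opening sentence |
| Contraception, men | before study entry | L + 3 months | 2.1.1.9; 14.1.6.1 |
| Follow-up of partner-pregnancy outcomes | L + 3 months | not stated | 8.6.2, second paragraph |
| Follow-up of participants' own pregnancies | no restriction | no restriction | 8.6.1 |

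**Step 1: overlap.** The precaution period ends at L + 3 months and the follow-up period begins at L + 3 months. They share only that boundary. A pregnancy conceived on treatment, or before L + 3 months, falls outside the follow-up sentence.

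**Step 2: does the result depend on what is meant by the study?** Section 3.6.2 collects survival until 1 year after the last dose. If being in the study included that time, the precaution period would run to about L + 12 months and would overlap the follow-up period from month 3 to month 12. The pregnancies of interest, from treatment to L + 3 months, would still lie outside follow-up.

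**Step 3: does the word for when a pregnancy occurs rescue the sentence?** It could be stretched to include a pregnancy conceived earlier and still continuing at L + 3 months. That is not the natural reading, and a pregnancy that had ended by then would still be left out.

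**Step 4: does another section require the missing follow-up?**

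- Section 8.6.1 concerns a participant who becomes pregnant. Its outcome rule and deadlines are not carried into 8.6.2.
- Adverse event recording (6.1) and serious adverse event reporting (8.3) would not pick up the pregnancy itself, because 8.6.2 says it is not an adverse event.
- Section 2.1.1.9 has a notification line, "Should a woman become pregnant or suspect she is pregnant while she or her partner is participating in this study", under which the woman is to tell her treating physician. It says nothing about tracing the outcome.
- Contraception is reviewed during treatment, at end of treatment and at the 30-day visit (3.4, 3.7). That may bring a pregnancy to light but does not ask for its outcome.
- The registry in 8.6.2 is voluntary for the partner, and the protocol says only that it may be offered.

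None of these requires follow-up of a partner pregnancy conceived during paternal exposure.

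**The case against.** The best reply is that this is a slip of a preposition. The section is headed as paternal exposure and opens with the right period. The follow-up sentence is only a best-effort request, and sensible staff would read through it. Section 8.6 also sends pregnancy reports and follow-up to sponsor forms and instructions that are not part of these documents and may handle the matter properly. Much of this stands. The sentence does look like a slip, and practice cannot be judged from the protocol alone. But the protocol is the text that staff are held to, and as worded it points them to the wrong period.

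Three stronger readings are tempting, and the documents do not support them.

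- A reader might infer that every exposed partner pregnancy will be lost. The sentence does not bar following them, and the registry and the notification line in 2.1.1.9 could catch some. The accurate statement is that follow-up is not required.
- A reader might infer that the trial loses its only human data on fetal effects. Section 8.6.1 requires outcomes for pregnancies in participants, which bear on fetal risk more directly. What is weakened is information on exposure through the father.
- A reader might multiply out the 12-cycle maximum and report a long uncovered stretch of days. That describes a man who completes the maximum course without delay, while Section 12.3.3 gives a median survival of at most 3 months in this setting. The figure would overstate a point that rests on wording alone.

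**Conclusion.** The inconsistency is real and lies within one short section. The precaution and follow-up periods for male participants meet only at 3 months after the last dose, so the follow-up request, taken literally, omits pregnancies conceived during paternal exposure and covers those conceived afterwards.

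Its practical size is small. The trial needs 25 evaluable participants of both sexes, contraception is required and the prognosis is poor. The documents give no expected number of partner pregnancies; very few is a judgement from those facts. The disease control rate, PFS, OS, the two-stage design and the sample size are untouched.

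The conclusion assumes that the sentence means what it says and that no sponsor instruction outside these documents overrides it. It takes no view on whether 3 months is the right length of precaution; it asks only that the section agree with itself. The point merits correction because the text is a working safety-reporting instruction, not background.

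**What to change.** Reword the follow-up sentence in 8.6.2 so that it covers partner pregnancies occurring during the study and until 3 months after the last dose of Minnelide. That is the period already set in the section's opening sentence, and its 3-month end agrees with 2.1.1.9 and 14.1.6.1. Keep the start as that sentence has it. If the sponsor prefers a dated start, define it once and use it in both sentences.

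The cost is one phrase in the next amendment, with the IRB review that any amendment needs. No visit or procedure has to be added, since contraception review during treatment and at the 30-day visit, and remote contact about every 90 days for a year after the last dose, are already planned.

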### 8.7 REGULATORY REPORTING FOR STUDIES CONDUCTED UNDER CCR-SPONSORED IND

Following notification from the investigator, CCR, the IND sponsor, will report any suspected adverse reaction that is both serious and unexpected. CCR will report an AE as a suspected adverse reaction only if there is evidence to suggest a causal relationship between the study product and the adverse event. CCR will notify FDA and all participating investigators (i.e., all investigators to whom the sponsor is providing drug under its INDs or under any investigator's IND) in an IND safety report of potential serious risks from clinical trials or any other source, as soon as possible, in accordance to 21 CFR Part 312.32.

All serious events will be reported to the FDA at least annually in a summary format.

Version Date: 7/10/2025

